10.1 Primary Objectives

1. *To compare rates of all-cause mortality in the 180 days following enrolment for an episode of high risk diarrhoea without dysentery among children 2 to 23 months of age living in low resource settings who are randomized to receive a 3-day course of azithromycin or placebo.*

Period prevalence of death will be compared between randomly-assigned treatment groups using relative risk regression. Mortality will be defined as a binary variable and will be defined as any event of death from time of randomization to end of day 180. Time to death will not be considered. Censored individuals will be retained in the denominator. For the primary ITT analysis, the following model will be used:

$$E(Y|\text{randomisation arm}) = e^{(\beta_0 + \beta_1 X_{azm})}$$

where x_{azm} is an indicator variable specifying randomized to the azithromycin group ($x_{azm}=1$) or not ($x_{azm}=0$). The risk ratio comparing the risk of death in children randomized to azithromycin vs. placebo will be determined by e^β . The statistical significance of this comparison will be determined by Wald test.

If the baseline assessment of randomization reveals an imbalance in characteristics between the randomization arms, we will evaluate these characteristics as potential confounders in a sub-analysis secondary to the ITT. The following baseline characteristics will be evaluated for balance between randomization arms (median age, stunting prevalence, wasting prevalence, prevalence of “some” and “severe” dehydration, site [Bangladesh, India, Kenya, Malawi, Mali, Pakistan, Tanzania], hospital admission, and median duration of diarrhoea). Potential baseline confounders will be added stepwise in the relative risk model with randomization arm as follows:

$$e^{(\beta_0 + \beta_1 X_{azm} + \beta_i X_i)}$$

Where i are the baseline characteristic(s) included in the model. These will be maintained in the model if their inclusion in the model changes the hazard ratio by more than 10%. Also, in a sub-

analysis, separate analysis for each site (Bangladesh, India Kenya, Malawi, Mali, Pakistan, Tanzania) will be presented to describe differences in treatment effects between sites (no formal hypothesis tests within each site stratum will be performed).

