4.4 Sensitivity analyses examining potential baseline imbalances

We will report baseline characteristics of participants by trial allocation arm (Table 1), we will examine imbalance by trial arm, accepting that these arose by random chance, and will not conduct hypothesis tests for difference by allocation arm. However we will include any apparent imbalances in sensitivity analyses for all primary and secondary outcomes. In sensitivity analyses, we will include as model covariates characteristics which on univariable analysis are associated with the outcome of interest with a p-value <0.10 . If the point-estimates for the unadjusted and adjusted analyses of the primary outcomes differ by more than 10%, the adjusted analysis will be presented as primary.

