9.1 Primary outcome 1 - 180 day Mortality

We will report the unadjusted risk ratio (RR) of all-cause death by trial allocation arm, which will be the number of deaths over number of persons in each trial allocation arm, and report either a χ^2 -test of $[(\text{death/placebo})/(\text{death/azithromycin})]$ or a Z-test of the $\log[(\text{death/placebo})/(\text{death/azithromycin})]$.

We will examine the 180-day fatality by randomized treatment groups using log-binomial mixed effects models to calculate the risk ratio and 95% confidence bound. Models will include trial site indicators as fixed effects to account for the randomization schema. The primary analysis would only include site as this is the stratified randomization factor. Fatality effect estimates will be presented in Table 2.

Regression model for the outcome of mortality in the ABCD trial will be defined as the following log-binomial mixed effects model:

$$\log Pr(Y_i = 1) = \beta_{0c} + \beta_1 C_i + \beta_2 Z_i \times 1_{\{t>t_0\}} + \varepsilon_i$$

– Model 1

Where

$$Y_i = \begin{cases} 1 & \text{died} \\ 0 & \text{alive at day 180} \end{cases}$$

And

$$\beta_{0c} = \beta_0 + b_c$$

Under this definition we are accounting for clustering at clinic level. The b term is a random effects for the c^{th} clinic, and take account of the variance due to clustering within clinic.

The term $\beta_1 C_i$ is the fixed effect of country, with C_i representing the country of enrolment for child i .

The term $\beta_2 Z_i$ is the fixed effect of azithromycin, with Z_i representing the treatment allocation for child i where

$$Z_i = \begin{cases} 1 & \text{azithromycin} \\ 0 & \text{placebo} \end{cases}$$

The term ε_{ij} is the variance component due to random error for child i at time j .

Now if $\mu_i = \log Pr(Y_i = 1)$ then Y is distributed as

$$Y_i \sim \text{Binomial}(\mu_i | b_c)$$

and Relative Risk of death by $Z_i = \exp(\beta_1)$

Extending Model 1 to admit child level covariates, we have:

$$\log Pr(Y_i = 1) = \beta_{0c} + \beta_1 C_i + \beta_2 Z_i \times 1_{\{t > t_0\}} + \beta_3 X_{ij} + \varepsilon_{ij}$$

- Model 2

Where X_{ij} is the vector of effect-modifying covariates of child i at time j :

$$X_{ij} = \begin{cases} \text{age category } (< 6m, 6 - 11m, \geq 12m) \\ \quad + \text{Sex} \\ \quad + \text{Reason for enrolment} \quad \quad \quad \text{(See Section 4.5)} \\ \quad + \text{Wealth quintile} \end{cases}$$

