9.2 Primary outcome 2 - Change in Length-for-age z-score

The group means at baseline and endline and the mean ΔLFAZ will be presented by treatment group in Table 3. We will use generalized linear mixed models with ΔLAZ as the response variable and treatment group, fixed effects for study site and variable effects for child (which accounts for baseline LAZ) and clinic as the explanatory variables.

The primary analysis for this variable will only include the site since this is the stratified randomization..

Regression model for the outcome change from baseline in length for age Z-score (Δ LFAZ) in the ABCD trial is defined as the following linear mixed-effects model:

$$Y_{ij} = \beta_{0_{c_i}} + \beta_1 C_i + \beta_2 Z_i \times 1_{\{j=1\}} + \varepsilon_{ij} \quad \text{- Model 3}$$

Y_{ij} is Δ LFAZ in child i at time j , where

$$j = \begin{cases} 1 & \text{day 90} \\ 0 & \text{enrollment} \end{cases}$$

$\beta_{0_{c_i}}$ is the random effect of child i at clinic c , where

$$\beta_{0_{c_i}} = \beta_0 + b_{c_i} + b_{0_i}$$

Under this definition we are accounting for clustering at clinic level and at child level. The b terms are random effects for the c^{th} clinic and the i^{th} child, and take account of the variance due to clustering within clinic or over time in a given child. The latter is effectively also an adjustment for baseline LFAZ and WFAZ for that child. Should these models not converge, we will allow clinic to remain the random effect, but adjust for baseline LFAZ as a fixed effect.

The term $\beta_1 C_i$ is the fixed effect of country, with C_i representing the country of enrolment for child i .

The term $\beta_2 Z_i$ is the fixed effect of azithromycin, with Z_i representing the treatment allocation for child i where

$$Z_i = \begin{cases} 1 & \text{azithromycin} \\ 0 & \text{placebo} \end{cases}$$

The term ε_{ij} is the variance component due to random error for child i at time j .

Participants whose Day 90 visit occurred outside the protocol defined window will be included in the Intention to Treat Analysis. Sensitivity analysis will take account of the time varying nature of this visit by fitting a model that allows the effect of azithromycin to vary as a function of time is:

$$Y_{ij} = \beta_{0_{c_i}} + \beta_1 C_i + \beta_2 Z_i \times 1_{\{t>t_0\}} + \beta_3 Z_i t_{ij} \times 1_{\{t>t_0\}} + \varepsilon_{ij}$$

- Model 4

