9.3 Analysis of secondary objectives 1, 2 and 3 - Hospitalization

Following an episode of high risk diarrhea without dysentery among children 2 to 23 months of age living in low resource settings who are randomized to receive a 3-day course of azithromycin or placebo, comparison by trial allocation arm of:

1. proportion of children hospitalized or died in the initial 10 days following enrolment.
2. proportion of children hospitalized in the 90 days following enrolment.
3. proportion of children hospitalized or died in the 90 days following enrolment.

Primary event considered will be the first episode of hospitalization per child. Hospitalization rates will be reported by country to understand heterogeneity across sites. Risk ratio will be estimated from a model including trial allocation and country of enrollment. Adjusted analysis will include effect modifying covariates, and sensitivity analysis will include unbalanced potential confounders by trial arm.

Hospitalization data are available as binary outcomes only, and date of hospitalization is missing for all events after 10 days of follow-up. Time to event analysis is not possible for the hospitalization outcome.

Since likelihood of hospitalization may cluster by clinic, the following log-binomial mixed effects model is proposed:

$$\log \Pr(Y_i = 1) = \beta_{0c} + \beta_1 C_i + \beta_2 Z_i \times 1_{\{t>t_0\}} + \varepsilon_i \quad - \text{Model 6}$$

Where

$$Y_i = \begin{cases} 1 & \text{hospitalized at least once by day 180} \\ 0 & \text{not hospitalized} \end{cases}$$

Under this definition we are accounting for clustering at clinic level. The b term is a random effects for the c^{th} clinic, and take account of the variance due to clustering within clinic.

The term $\beta_1 C_i$ is the fixed effect of country, with C_i representing the country of enrolment for child i .

The term $\beta_2 Z_i$ is the fixed effect of azithromycin, with Z_i representing the treatment allocation for child i where

$$Z_i = \begin{cases} 1 & \text{azithromycin} \\ 0 & \text{placebo} \end{cases}$$

The term ε_{ij} is the variance component due to random error for child i at time j .

Adjusted analysis will include individual level effect modifiers, thus:

$$\log \Pr(Y_i = 1) = \beta_{0c} + \beta_1 C_i + \beta_2 Z_i \times 1_{\{t>t_0\}} + \beta_{3X} \mathbf{X}_{ij} + \varepsilon_i \quad - \text{Model 7}$$

Where \mathbf{X}_{ij} is the vector of effect-modifying covariates of child i at time j :

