Figure 1. Participant flow in CONSORT recommended format (Lancet 2001; 357: 1193)

ABCD Consort Flow Diagram

Tables

Table 1. Participant characteristics at enrolment by trial allocation arm

Variable	Placebo	Azithromycin
Number of participants	xxx	xxx
Mean (SD) age, months	xx.x (xx.x)	xx.x (xx.x)
Proportion male, %	xx.x%	xx.x%
Mean (SD) weight, kg	xx.x (xx.x)	xx.x (xx.x)
Mean (SD) length, cm	xx.x (xx.x)	xx.x (xx.x)
Mean (SD) MUAC, cm	xx.x (xx.x)	xx.x (xx.x)
Mean (SD) LAZ, z-score units	xx.x (xx.x)	xx.x (xx.x)
Mean (SD) WLZ, z-score units	xx.xx (xx.xx)	xx.xx (xx.xx)
Prevalence of moderate stunting (-3.0<LAZ≤-2.0), %	xx.xx (xx.xx)	xx.xx (xx.xx)
Prevalence of severe stunting (LAZ≤-3.0), %	xx.xx (xx.xx)	xx.xx (xx.xx)
Prevalence of moderate wasting (-3.0<WLZ≤-2.0), %	xx.xx (xx.xx)	xx.xx (xx.xx)
Prevalence of some or severe dehydration, %	xx.xx (xx.xx)	xx.xx (xx.xx)
Mean (SD) maternal age, years	xx.x (xx.x)	xx.x (xx.x)
Mean (SD) maternal height, cm	xx.x (xx.x)	xx.x (xx.x)
Mean (SD) maternal weight, kg	xx.x (xx.x)	xx.x (xx.x)
Mean (SD) maternal BMI, kg / m ²	xx.x (xx.x)	xx.x (xx.x)
Mean (SD) maternal MUAC, cm	xx.x (xx.x)	xx.x (xx.x)
Mean (SD) maternal education, years	xx.x (xx.x)	xx.x (xx.x)
Mean (SD) number of children below 5 years of age in the household	xx.x (xx.x)	xx.x (xx.x)

SD = standard deviation; MUAC = mid-upper arm circumference; LAZ = length-for-age Z-score; WLZ = weight-for-length Z-score; BMI = body mass index

Table 2. Primary outcomes

Outcome	Placebo	Azithromycin	RR (95% CI)*	p-value
180 day mortality	n/N (%)	n/N (%)		
ΔLAZ mean (sd)		NA		

* from adjusted generalized linear mixed model

RR = Risk Ratio; CI = confidence interval; ΔLAZ = mean change in length-for-age Z-score

Table 3. Anthropometric parameters

Anthropometric parameter	Placebo	Azithromycin	Effect (95% CI)	P-value
Day 90 anthropometry performed, N (%)				
LAZ at day 90, Mean (sd)				
WAZ at day 90, Mean (sd)				
ΔWAZ (95%CI)				
WLZ at day 90, Mean (sd)				
ΔWLZ (95%CI)				
MUAC at day 90 (cm), Mean (sd)				
ΔMUAC (95%CI)				

Δ = mean change in anthropometric parameter between day 1 and day 90; LAZ = length-for-age Z-score; WAZ = weight-for-age Z-score; WLZ = weight-for-length Z-score; MUAC = mid-upper arm circumference

Table 4. Secondary outcomes

Outcome	Placebo	Azithromycin	RR (95% CI)*	Wald test p-value
Day 10 hospitalization or death	n/N (%)	n/N (%)		
Day 90 hospitalization or death	n/N (%)	n/N (%)		
Day 90 hospitalization	n/N (%)	n/N (%)		

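### SAP 4.4 promotes a covariate-adjusted model to primary after a 10% shift, against SAP 9.1, SAP 9.2 and protocol 10.1, and the covariate-selection rules conflict

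*SAP*

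**What the plan says.** **Which model is primary**

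- SAP 4.4, a section on sensitivity analyses, ends with a switch. If unadjusted and adjusted point estimates of the primary outcomes "differ by more than 10%, the adjusted analysis will be presented as primary".
- SAP 9.1 (mortality): "The primary analysis would only include site as this is the stratified randomization factor".
- SAP 9.2 (ΔLAZ): "The primary analysis for this variable will only include the site since this is the stratified randomization". Both sections place imbalanced covariates in sensitivity analysis, and neither refers to 4.4.
- Protocol 10.1 fits the primary ITT models with the arm indicator alone. Imbalanced characteristics are examined as "potential confounders in a sub-analysis secondary to the ITT". The same status is given to adjustment for ΔLAZ.

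**What the labels mean**

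- SAP 9.1: "We will report the unadjusted risk ratio (RR) of all-cause death by trial allocation arm". This is the crude ratio, yet SAP 4.3 puts country in every primary and secondary analysis.
- The footnote to the risk-ratio column of SAP Table 2 (primary outcomes) reads "from adjusted generalized linear mixed model".
- SAP 9.3 uses the word in another sense: "Adjusted analysis will include effect modifying covariates". Imbalance models are listed separately there.

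**Which covariates enter**

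- SAP 4.4 rules out between-arm hypothesis tests, includes apparent imbalances, and selects on univariable association with the outcome at p<0.10.
- SAP 9.1 selects on a between-arm t-test or χ² test at p<0.2.
- Protocol 10.1 enters covariates stepwise. For mortality: "These will be maintained in the model if their inclusion in the model changes the hazard ratio by more than 10" per cent, although the model is a risk-ratio model. For ΔLAZ the same threshold applies to the difference in means.

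**The concern.** A primary analysis should be identifiable before the data are seen. Here the default model is stated twice, but a clause elsewhere in the same SAP can displace it, depending on how far the estimate moves. A statistician who reaches that clause must decide what *unadjusted* means (crude, or with country), what *adjusted* means, and which covariate rule feeds the comparison. Two competent statisticians could follow the text and report different primary results.

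This matters most for ΔLAZ. SAP section 2 records that the DSMB had already seen a statistically significant LAZ difference, which it thought clinically less relevant. The target difference is so small that 10% of it is only 0.004 z.

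**Working it through.** **Inputs from protocol 10.3.** ΔLAZ: difference 0.04, SD 0.6 or 0.7. Mortality: control risk 2.7%, relative risk 0.65. Both: 5,750 per arm, 10% loss. R², the share of outcome variance that the added covariates explain beyond the primary model, is not in the documents. It is assumed at 1, 5, 10 and 20%.

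**The plan's own figures reproduce.**

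- ΔLAZ, n = 2(z₁₋α/₂ + z₁₋β)²SD²/δ²: with SD 0.7 and 80% power, 2 × 7.849 × 0.49/0.0016 gives 4,808 (stated 4,809). With SD 0.6 and 90% power the result is 4,729 (stated 4,730).
- Mortality: 5,123 per arm, and 5,123/0.9 = 5,693 (stated 5,696).

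**How often the switch fires for ΔLAZ.** With 5,750 × 0.9 = 5,175 per arm, SE = SD × √(2/5,175) = 0.0118 (SD 0.6) or 0.0138 (SD 0.7). Let the adjusted estimate be a = τ + h and the unadjusted u = τ + g + h, with var(g) = SE²R² and var(h) = SE²(1 − R²). The switch fires if |a − u| > 0.1|u|. The shift has standard deviation SE√R², about 0.001 to 0.006 z. Simulation with a fixed covariate set and τ = 0.04:

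| R² | Fires, SD 0.6 | Fires, SD 0.7 | Fires and changes significance, SD 0.6 | Same, SD 0.7 |
|---|---|---|---|---|
| 1% | 2% | 4% | 0.2% | 0.3% |
| 5% | 16% | 23% | 1.8% | 3.1% |
| 10% | 30% | 38% | 3.0% | 5.4% |
| 20% | 45% | 52% | 4.6% | 8.4% |

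In these runs the switch removes significance in at most 1.7% of trials whose unadjusted result was significant. Most changes run the other way.

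**Given an observed z.** With no prior information on τ, P(fires) = 2Φ(−0.1|z|/√R²), whatever the sample size and SD. For R² of 1, 5 and 10% this is 5, 37 and 53% at z = 2, and 0.3, 18 and 34% at z = 3.

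**Type I error (τ = 0).** The mechanical rule with fixed covariates rejects in 4.4 to 5.0% of trials. Free choice of whichever model is significant rejects in about 5.5 to 7.1%.

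**Mortality on the risk-ratio scale.** Missing outcomes count as alive, so n = 5,750 per arm. Expected deaths are 5,750 × 0.027 = 155.3 and 5,750 × 0.01755 = 100.9. SE(log RR) = √(1/155.3 + 1/100.9 − 2/5,750) = 0.127. At R² 10% the log shift has SD 0.127 × √0.10 = 0.040, and the risk ratio moves by more than 10% in about 1% of trials. A child-level simulation with seven covariates (combined c-statistic 0.69 to 0.81, control risk from 2.7% down to an assumed 0.5%) gives 0 to 2.5%. It used a Poisson model without country or clinic terms, so it only approximates the SAP 9.1 model.

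**The case against.** **SAP 4.4 may be a prespecified exception.** It could be read as a conditional override of the 9.1 and 9.2 default, with the protocol section only an outline that the SAP may refine. This has some force: a default is clearly stated, so it would be wrong to infer that the SAP names no primary model. But 9.1 and 9.2 carry no exception, SAP 10.5 promises the primary outcomes in their planned form, and the version history of SAP 1.0 claims alignment with the protocol. The override also cannot be carried out as written, because its reference model is undefined and its covariate rule conflicts with 9.1.

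**Firing is not consequence.** This stands. The shifts are small, and the switch changes significance far less often than it fires.

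**The scale of the 10% is clear enough for mortality.** This largely stands. A reader might infer that the switch is likely for mortality too, because on the log risk-ratio scale it would fire often. The documents never mention that scale: SAP 9.1 and Table 2 report a risk ratio, and the protocol's 10% rule is applied to a ratio. Risk-ratio firing rates of 13 to 29% arise only if R² is 10% at control risks of 1.0 to 0.5%. That needs very strong predictors, with a c-statistic of about 0.87 to 0.90.

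**Conclusion.** The contradiction stands on the text alone and should be fixed. SAP 4.4 makes the primary estimate depend on the data in a way that SAP 9.1, SAP 9.2 and protocol 10.1 do not allow, and three covariate rules compete to feed it.

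The practical effect is modest and falls mainly on ΔLAZ. The firing rates rest on assumed R², a fixed covariate set, a normal approximation, the protocol SDs taken as residual SDs of the primary model, and planned numbers. Recruitment stopped early, so the actual SE is larger than used here and firing somewhat more frequent.

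A reader might infer that the switch inflates type I error. With fixed covariates it does not. The 5.5 to 7.1% arises only if the team picks whichever model is significant, which the SAP does not propose; the loose wording merely fails to exclude it. Data-driven selection under the conflicting covariate rules is outside these runs.

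A reader might also tie this to SAP 6.3 and 6.4, where masked by-arm results may prompt SAP amendments. That is a separate question, and this point does not depend on it.

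**What to change.** 1. Delete the last sentence of SAP 4.4. State that the 9.1 and 9.2 models are primary whatever the adjusted result: treatment, country as a fixed effect and clinic as a random effect. For ΔLAZ add baseline LAZ as a fixed covariate; this is the ANCOVA form in SAP 4.6 and the fallback already in 9.2.
2. Label the crude risk ratio in 9.1 as descriptive, and make the Table 2 footnote name the country- and clinic-adjusted primary model.
3. Delete the p<0.10 screen in 4.4 and the p<0.2 imbalance test in 9.1. Use one closed, prespecified list for the sensitivity analysis, drawn from the protocol 10.1 candidates plus sex: age, sex, stunting, wasting, dehydration, hospital admission and duration of diarrhoea. Country is already in the primary model, and so is baseline LAZ for ΔLAZ. State that the list replaces the protocol's stepwise 10% rule.
4. As a separate drafting correction in 9.1, give the risk ratio as azithromycin over placebo and as exp(β₂). As written the ratio is inverted and exponentiates β₁, the country term.

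The cost is SAP wording only; sample sizes do not change. The downside is that a slightly more precise adjusted estimate stays a sensitivity result.

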4.5 Effect modification of treatment effects

We will examine whether treatment effects on the outcomes (primary and secondary) differ by *a priori* determined effect modifiers. We will examine modification of treatment effects by trial site by including effect modifying covariates in the regression models.

Effect modifiers of interest include:

1. The participant's age (examined as a continuous variable, but reported as <6 months of age, 6-11 months, 12 months or older)
2. The participant's sex
3. Reason for enrolment: dehydration, moderate wasting or severe stunting considered as non-mutually exclusive categories
4. Participant's wealth quintile with respect to country-specific national wealth distribution (see derivation in Section 7.7)

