Model 4 allows for a proportional effect of fixed magnitude (parameter β_2) *and* for a time-varying effect (parameter β_3).

Under Model 2 the term $\beta_{0_{ci}}$ is the random effect of child i at clinic c , as it was above, but where

$$\beta_{0_{ci}} = \beta_0 + b_{ci} + b_{0i} + b_{1i}t_{ij}$$

As before, should these models fail to converge, we will allow clinic to remain the random effect, but adjust for baseline LFAZ as a fixed effect.

Extending Model 4 to admit child level covariates, we have:

$$Y_{ij} = \beta_{0_{ci}} + \beta_1 C_i + \beta_2 Z_i \times 1_{\{t > t_0\}} + \beta_3 Z_i t_{ij} \times 1_{\{t > t_0\}} + \beta_4 \mathbf{X}_{ij} + \varepsilon_{ij}$$

- Model 5

Where \mathbf{X}_{ij} is the vector of effect-modifying covariates of child i at time j :

$$\mathbf{X}_{ij} = \begin{cases} \text{age category } (< 6m, 6 - 11m, \geq 12m) \\ \quad + \text{Sex} \\ \quad + \text{Wealth quintile} \end{cases}$$

Where randomization resulted in imbalanced covariates, sensitivity analysis will include in vector \mathbf{X}_{ij} confounders that are imbalanced (e.g. but not limited to: sex, wasting, stunting, dehydration) as previously described.

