9.4.1 Outcome Definitions

1. Δ WLZ = WLZ at endline visit *minus* WLZ at randomization visit
2. Δ WAZ = WAZ at endline visit *minus* WAZ at randomization visit
3. Δ MUAC = MUAC at endline day visit *minus* MUAC at randomization visit

In sensitivity analysis the endline visit date will be restricted to those who had the visit from study day 91 to 100.

The group means for WLZ, WAZ and MUAC at baseline, endline and mean change will be presented by group as indicated in Table 3. We will use generalized linear mixed models with Δ WLZ, Δ WAZ or Δ MUAC as response variables and treatment group and fixed effects for study country and random effects for clinic and child as the explanatory variables. A sensitivity analyses including potential effect modifiers and unbalanced confounders will be done. Modeling will be analogous to Models 3-5 listed in Section 9.2, but where Y_{ij} is Δ WLZ, Δ WAZ or Δ MUAC respectively, in child i at time j .

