10.1 Time-to-event analysis of mortality

Time-to-event sensitivity analyses will be conducted. We will construct stratified Kaplan-Meier curves to graphically present the timing of participant deaths by treatment group. The stratified log rank test will be used to assess statistical difference between treatment groups to account the stratified randomization. We will also use Cox proportional hazard models with fixed effects for trial site to produce hazard ratio estimates. Date of loss to follow-up will be date of last recorded contact, and will censor further analysis.

Mean anthropometry at enrolment and other baseline covariates will be described for the cohort of deceased children. Given small number of deaths, further analysis (e.g. of effect modification of child level covariates or of seasonality on death outcome) may not be appropriate.

10.2 Outcome by age: Models will be constructed for restricted age bands (<6 months, 6-11 months, 12 months and older). In such models age will not be incorporated into vector X_{ij} .

10.3 Outcome by reason for enrolment: Models will be constructed separately for participants enrolled for severe stunting, for moderate wasting and for dehydration.

10.4 Seasonality by country may be explored by adding a spline term to the models outlined, allowing outcome to vary seasonally by country.

10.5 Heterogeneity across countries may be expected to occur in underlying population (e.g. proportion stunted at baseline) and also for some trial outcomes. Heterogeneity may be explored by presenting country specific model as a forest plot, and using meta-analytic techniques providing a pooled weighted estimate, and heterogeneity metrics such as the I^2 statistic. Metaregression could be used to explore magnitude of impact of heterogeneous covariates. Although heterogeneity will be explored, stratum specific testing is not envisaged (apart from adjusted models already described) as there is unlikely to be adequate power to test within a stratum. We will present the results of our defined Primary Outcomes as planned, describing any apparent heterogeneity.

[figure not shown]
11 Software

Software: The study statistician will employ the software that s/he is experienced with using. The analyses provided by the statistician (on the direction of the site PIs) will be considered final. No parallel analyses of the same data/ question will be considered.

12. Figures and tables

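### The covariate models enter the SAP 4.5 effect modifiers only as main effects, so as written they cannot show whether the azithromycin effect differs between subgroups

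*SAP*

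**What the plan says.** SAP 4.5 states the aim: "We will examine whether treatment effects on the outcomes (primary and secondary) differ by" modifiers fixed in advance. It lists four at child level: age (analysed as continuous, reported in three bands), sex, reason for enrolment and wealth quintile. The third is entered as "Reason for enrolment: dehydration, moderate wasting or severe stunting considered as non-mutually exclusive categories".

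The later sections carry these variables as follows.

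- **Mortality (SAP 9.1, Model 2).** The vector X_ij holds age band, sex, enrolment reason and wealth quintile, and enters as β3·X_ij.
- **ΔLAZ (SAP 9.2, Model 5).** X_ij "is the vector of effect-modifying covariates of child" i; it holds age band, sex and wealth quintile, and enters as β4·X_ij.
- **Hospitalization (SAP 9.3, Model 7).** The text says "Adjusted analysis will include effect modifying covariates, and sensitivity analysis will include unbalanced potential confounders by trial arm". The model is introduced by "Adjusted analysis will include individual level effect modifiers, thus", with the same three variables.
- **ΔWLZ, ΔWAZ, ΔMUAC (SAP 9.4.1).** "Modeling will be analogous to Models 3-5 listed in Section 9.2".

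The exploratory section adds two stratified analyses. In 10.2, "Models will be constructed for restricted age bands". In 10.3, "Models will be constructed separately for participants enrolled for severe stunting, for moderate wasting and for dehydration". SAP 10.1 warns that modifier analysis of deaths may not be appropriate because deaths are few, and 10.5 offers an optional look at heterogeneity between countries.

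**The concern.** A covariate added as a main effect moves the expected outcome up or down for a subgroup. It does not let the treatment effect differ between subgroups; only a product of treatment and covariate does that. Calling X_ij effect-modifying does not change what the equation estimates. An analyst who follows the equations will have no parameter that answers the question in 4.5.

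The question matters here. The Protocol's rationale is targeted antibiotic use in defined high-risk children, so a difference by enrolment reason bears directly on it. The SAP introduction reports that the DSMB saw a LAZ difference that was statistically significant but of less clinical relevance, which makes it natural to ask who benefits. SAP 6.6 foresees changes to models after the first results. If the interaction terms, scale and reporting are not fixed beforehand, any subgroup statement becomes a post hoc choice.

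**Working it through.** **1. Where treatment Z appears in each model**

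| Model | Terms containing Z | Terms containing X | Z×X? | Enrolment reason in X? |
|---|---|---|---|---|
| 2, mortality | β2·Z × post-baseline indicator | β3·X | No | Yes |
| 5, ΔLAZ | β2·Z × post-baseline indicator; β3·Z × time | β4·X | No | No |
| 7, hospitalization | β2·Z × post-baseline indicator | β3·X | No | No |
| Wasting (as Models 3-5) | as Model 5 | as Model 5 | No | No |

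Models 4 and 5 write the treatment-by-time product out in full, so the absence of Z×X is hard to read as shorthand. X also uses age bands, where 4.5 says continuous age.

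**2. What 10.2 and 10.3 add.** The age bands are disjoint, so the difference between two separate fits equals the Z×band coefficient (0.0599 both ways in one simulated trial). A comparison can be derived, although none is stated. The enrolment-reason groups overlap, so separate fits are not independent and there is no estimate for children without a given reason. Sex and wealth do not appear.

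**3. The Protocol's own subgroup figure.** Protocol 10.3 claims 90% power for a ΔLAZ difference of 0.06 within infants and, separately, within toddlers. With n = 2·(1.960+1.282)²·SD²/δ², SD 0.7 and δ 0.06, n = 2,861 per group; Table 1 gives 2,862. This concerns the effect within one age group, not the difference between two.

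**4. Power for ΔLAZ interactions.** Inputs: SD 0.6 and 0.7, 5,750 per arm and 10% loss (Protocol 10.3); two-sided alpha 0.05. Clinic and country terms are ignored. With n per arm and modifier prevalence p:

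SE = SD·√(2/(n·p·(1−p))); detectable difference at 80% power = 2.80·SE.

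| n per arm | p | SD 0.6 | SD 0.7 |
|---|---|---|---|
| 5,750 | 0.5 | 2.80 × 0.0224 = 0.063 | 2.80 × 0.0261 = 0.073 |
| 5,175 (10% loss) | 0.5 | 0.066 | 0.077 |
| 2,875 (assumed half of plan) | 0.5 | 0.089 | 0.103 |
| 5,750 | 0.2 | 0.078 | 0.091 |

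For lowest against highest wealth quintile, assuming equal fifths, SE = SD·√(20/n), giving 0.099 and 0.116 at 5,750 per arm.

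**5. Illustration (assumed effects).** Suppose the true effect is 0.08 in one sex and 0.00 in the other. In 3,000 simulated trials at 5,750 per arm, the main-effects model returned 0.040 for everyone. With Z×sex the estimates were 0.00 and 0.08, and the interaction was detected in 94.5% (SD 0.6) or 86.3% (SD 0.7) of trials; the closed form gives 94.7% and 86.5%. If the sexes differ by only 0.04, power is 43% or 33%.

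**6. Hospitalization.** The documents give no risk, so r = 3% to 10% is assumed. For a 50/50 modifier at 5,750 per arm, the SE of the log ratio of risk ratios is √(4(1−r)/(r·n/2)). The detectable ratio, exp(2.80·SE), is 1.81 at 3%, 1.58 at 5% and 1.37 at 10%.

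**The case against.** The best defence is that 4.5 promises to examine, not to test. SAP section 5 states no interaction hypothesis, and 10.5 says testing within strata is not envisaged because power is unlikely to be adequate. Estimates by subgroup without p-values would fit that stance, and 10.2 and 10.3 supply them for two of the four modifiers. This stands in part: the lack of a named test is not by itself a breach of 4.5. But the printed models give no subgroup-specific effect either, and for sex and wealth nothing else does.

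A second defence is that this is a notation slip. The SAP labels X_ij effect-modifying, and 10.5 excepts the adjusted models already described from its remark on stratum testing, which suggests that the authors thought those models covered the question. That may well be so, and it makes the correction easier. The equations still need correcting.

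Three further objections stand and limit the remedy.

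- Inclusion requires at least one of the three enrolment reasons, so children without dehydration are all wasted or severely stunted. Testing the reasons one at a time would mix them.
- 4.5 covers all secondary outcomes, yet SAP 9.5.3 and 9.6.4 use its variables for the resistance outcomes only as possible confounders.
- Low power is real, and the 0.08/0.00 case is an illustration, not evidence of harm.

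A reader might infer that the treatment comparisons are compromised, or that the SAP holds no subgroup information at all. Neither follows. The primary analyses use models without X_ij, and 10.2 and 10.3 do give estimates.

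**Conclusion.** The point holds for the covariate models of mortality, ΔLAZ, hospitalization and wasting. It rests on the form of the equations, not on a numerical assumption. For age and enrolment reason the SAP has exploratory subgroup estimates but no comparison between groups. For sex and wealth, the question raised in 4.5 cannot be answered from any stated child-level analysis. A single estimate from these models must not be read as evidence that the effect is uniform.

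The power figures depend on the Protocol SDs, on ignoring clinic and country terms, and on the planned number. Recruitment stopped early and the documents do not give the final number; half of plan is only an assumed case. For enrolment reasons entered jointly, the one-modifier figures are a best case, because overlap between the reasons can only widen the standard errors. The correction should be made, but its results can only be exploratory.

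**What to change.** For ΔLAZ, ΔWLZ, ΔWAZ, ΔMUAC and the three hospitalization endpoints, add treatment-by-modifier terms in separate models for:

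- (a) age, continuous as 4.5 states, with band-specific effects from a Z×band version or from the 10.2 fits;
- (b) sex;
- (c) wealth quintile, stating whether it enters as a trend or as categories;
- (d) enrolment reason, with the three yes/no indicators and their products with Z entered together.

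State the scale: mean difference for anthropometry, ratio of risk ratios for hospitalization. Report subgroup estimates and interaction estimates with 95% confidence intervals and p-values, labelled exploratory, low-powered and unadjusted for multiplicity. Give the detectable differences, recalculated at the final number. SAP 9.1 and 9.3 name no fallback if a log-binomial model fails to converge, so name one.

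For mortality, correct Model 2 in the same way, but fit interactions only where event counts allow, in line with 10.1. For the resistance outcomes, either add the same terms or state that 4.5 does not apply to them. Leave country to 10.5.

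The cost is wording and model terms; no new data are needed. The downside is more exploratory tests. One overall test for each of four modifiers on seven outcomes makes 28, with 28 × 0.05 = 1.4 expected below 0.05 by chance if no interaction exists. Separate p-values for each enrolment reason make 6 × 7 = 42, with 2.1 expected. Mortality and resistance are not in these counts.

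A separate correction, which adds no weight to this point: SAP 9.1 gives the relative risk of death by treatment as exp(β1), but it defines β1 as the country term and β2 as the azithromycin term. It should read exp(β2).
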